1.1 Efficacy of cytotoxic agents, anti-EGFR therapies in CRC

Antibodies that target the epidermal growth factor receptor (EGFR) have been studied in clinical studies primarily involving previously treated patients since the beginning of development. In a US phase II study, IMCL CP02-9923, patients with metastatic CRC unresponsive to chemotherapy including irinotecan, the response rate of combination therapy with irinotecan and cetuximab (Cmab) was 15.2%. BOND-1, a European phase II randomized study evaluated Cmab alone or in combination with irinotecan in patients with colorectal cancer unresponsive to chemotherapy including irinotecan, where the response rate was 22.9% and significantly higher in the combination group than 10.8% in the monotherapy group⁵. The progression-free survival was also improved in the combination group (4.1 vs. 1.5 months, respectively), despite the apparent resistance to irinotecan⁵. These findings suggest that anti-EGFR therapy can potentially re-induce irinotecan sensitivity in irinotecan resistant colon cancer. In the CO-17 study, Cmab monotherapy significantly prolonged survival time in patients with irinotecan-, fluoropyrimidine-, and oxaliplatin-resistant colorectal cancer, compared with best supportive care (BSC)⁶. Based on these findings, Cmab was approved for monotherapy or combination therapy with irinotecan for the treatment of irinotecan-resistant, EGFR-positive metastatic colorectal cancer in the US and Europe.

EPIC, a phase III study that consisted of 1298 patients with treatment refractory advanced CRC, investigated irinotecan monotherapy in comparison to the combination of irinotecan with Cmab as second-line treatment⁷. The combination group demonstrated a significant improvement in response rate (4.2% vs. 16.4%) and progression-free survival (2.6 vs. 4.0 months), but no difference in overall survival (10.9 months vs 10.0 months, combination versus monotherapy respectively). The lack of survival benefit may be attributed to the 46.9% of patients randomized to irinotecan monotherapy that received Cmab as post-study therapy. In the CRYSTAL trial, Cmab in combination with FOLFIRI demonstrated a significant improvement in response rate and progression-free survival compared to FOLFIRI⁸.

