1.3 Anti-EGFR antibody-related adverse events

EGFR may control proliferation and differentiation of keratinocytes in normal skin. Inhibition of EGFR results in cessation of proliferation and migration of keratinocytes, leading to apoptosis. In addition, inflammatory cytokines are released, and the entire epidermis may become thin, fragile, vulnerable, and unable to retain moisture¹⁶. Rash acneiform is the most common skin disorder, and usually occurs within 1 to 3 weeks after administration of an anti-EGFR antibody. The most commonly affected area is the upper trunk, including the face, anterior chest, back, and forearm. The severe rash acneiform is often associated with itching and pain. It is replaced by skin dryness and cracking approximately 4 weeks after administration. Paronychia characterized by impaired nail growth and periungual pain may occur 8 weeks or later and be complicated by granulation or abscess in serious cases^{16,17}. Grade 3 or higher skin toxicity has been reported in 9.4% to 16.7% of patients treated with cetuximab⁵⁻⁸, partly contributing to

premature discontinuation of treatment. Another significant adverse drug reaction is severe infusion reaction, with an incidence of less than 5% and interstitial pneumonia (1-2%). In addition, hypomagnesemia, hypokalemia, and hypocalcemia have been reported, requiring monitoring of serum electrolytes before, during, and after treatment and appropriate supplementation as needed.

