1.4 Efficacy of regorafenib for colorectal cancer

Regorafenib is an oral multi-kinase inhibitor and inhibits receptor tyrosine kinases involved in neovascularization (VEGFR 1-3, TIE2), tumor microenvironment (PDGFR- β , FGFR), and oncogenesis (KIT, PDGFR, RET, BRAF)¹⁸. Regorafenib was recently shown to provide a survival benefit in metastatic colorectal cancer patients who have progressed after all standard therapies in the CORRECT trial¹⁹. This led to its approval in September 2012 by the FDA for use in the United States. Despite the observed benefits in a patient population with no current standard, toxicities such as Palmar-planter erythrodysesthesia syndrome (PPES) (which occurs early in the first 1-2 weeks) and fatigue have widely limited its use in the US¹⁹. ReDOS (Regorafenib dose optimization study), a randomized phase II trial, evaluated a dose escalation strategy compared to the standard dosing evaluated in the CORRECT study. The study demonstrated superiority in the proportion of patients who initiated the third cycle in the weekly dose escalation arm compared to patients who received standard dosing of 160mg per daily (43% vs 25%)²⁰. A survival benefit was also observed favoring the dose escalation arm (9.0 versus 5.9 months; p=0.094)²⁰. Based off these results, the NCCN has recommended the weekly dose-escalation strategy for regorafenib.

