2.2 Secondary

- 2.21 To compare the first progression free survival (PFS1) between patients with right sided (primary tumor) metastatic colon cancer who were randomized to receive regorafenib followed by anti-EGFR monoclonal antibody therapy compared to those that receive anti-EGFR monoclonal antibody followed by regorafenib.

- 2.22 To compare the second progression free survival (PFS2) between patients with right sided (primary tumor) metastatic colon cancer who were randomized to receive regorafenib followed by anti-EGFR monoclonal antibody therapy compared to those that receive anti-EGFR monoclonal antibody followed by regorafenib.

- 2.23 To compare the sequential treatment progression free survival (stPFS) between patients with right sided (primary tumor) metastatic colon cancer who were randomized to receive regorafenib followed by anti-EGFR monoclonal antibody therapy compared to those that receive anti-EGFR monoclonal antibody followed by regorafenib.

- 2.24 To assess the frequency and severity of adverse events between patients with right sided (primary tumor) metastatic colon cancer who were randomized to receive regorafenib followed by anti-EGFR monoclonal antibody therapy compared to those that receive anti-EGFR monoclonal antibody followed by regorafenib.

- 2.25 To compare the objective response rate (ORR), while on initial treatment, between patients with right sided (primary tumor) metastatic colon cancer who

were randomized to receive regorafenib followed by anti-EGFR monoclonal antibody therapy compared to those that receive anti-EGFR monoclonal antibody followed by regorafenib.

- 2.26 To compare the objective response rate (ORR), while on sequential treatment, between patients with right sided (primary tumor) metastatic colon cancer who were randomized to receive regorafenib followed by anti-EGFR monoclonal antibody therapy compared to those that receive anti-EGFR monoclonal antibody prior to regorafenib.

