Safety Population: The Safety Population comprises all patients who received any protocol treatment.

- 16.11 **Primary Endpoint:** The primary endpoint is overall survival. The primary objective for this trial is to compare the overall survival (OS) between evaluable patients who were randomized to arm A and arm B. Overall survival is defined as the time from randomization to death from any cause. Patients who are alive at the time of statistical analysis will be censored at the last known alive date.
- 16.12 **Secondary Endpoints:** Each secondary endpoint will be compared between arms. These include first progression free survival (PFS1), second progression free survival two (PFS2), sequential treatment progression free survival (stPFS), objective response rate of initial treatment and sequential treatment, and incidence of adverse events from initial treatment, sequential treatment and whole period.

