16.325 Sequential Treatment Objective Response Rate

The objective response rate to sequential treatment is defined as the number of patients who achieve a best response to sequential treatment of complete response or partial response (CR or PR) while on sequential treatment divided by the total number of evaluable patients who initiated sequential treatment. Point estimates and the corresponding 95% confidence intervals for the true success proportions will be calculated.

16.326 Adverse Events

Adverse events by patient will be summarized by frequencies and severity using CTCAE version 5.0. We will also closely monitor adverse events throughout the study.

16.327 Correlative Research

Serial blood collections – prior to cycle 1, every 8 weeks at the time of restaging scans and disease progression will be collected to post-hoc evaluate for plasma biomarkers prognostic or predictive to response and acquired treatment resistance

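### Adverse-event incidence by phase is compared between arms as a crude per-patient frequency over an open-ended time on drug, so time-accruing events may partly reflect exposure rather than risk

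*Combined protocol and SAP*

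**What the plan says.** Objective 2.24 is a between-arm harm objective: "To assess the frequency and severity of adverse events between patients with right sided (primary tumor) metastatic colon cancer". Section 16.12 states "Each secondary endpoint will be compared between arms" and lists among those endpoints "incidence of adverse events from initial treatment, sequential treatment and whole period". The denominator is defined in Section 16.1: "The Safety Population comprises all patients who received any protocol treatment".

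The whole method for this endpoint is one sentence in Section 16.326: "Adverse events by patient will be summarized by frequencies and severity using CTCAE version 5.0". It is followed only by a statement that adverse events will be monitored closely. There is no person-time rate, time to first event, cumulative incidence or fixed observation window, and no test is named.

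The length of a phase is not fixed. Under Section 13.4, patients without progression stay on treatment until they progress or cannot tolerate it. In the initial phase arm A receives regorafenib and arm B receives anti-EGFR therapy with or without irinotecan (Section 7.0). In the sequential phase the drugs are swapped.

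**The concern.** A per-patient frequency counts everyone who had the event at some point while on the drug. Someone treated for six months has had more opportunity to be counted than someone treated for two. Randomization does not balance this, because time on drug is itself a consequence of the assigned drug's efficacy and tolerability. A drug that controls disease longer could therefore look more toxic simply because patients remain on it.

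This matters because Section 1.9 offers the new sequence partly on the ground that its toxicity profile differs. Late events are the most exposed. Section 1.3 notes, for anti-EGFR antibodies, that "Paronychia characterized by impaired nail growth and periungual pain may occur 8 weeks or later". An event with that timing can be seen only in patients still under treatment at that point. Without time on treatment in the report, a reader cannot tell how much of a difference is exposure.

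**Working it through.** **Design figure.** The documents give no figure for the adverse-event comparison. The overall-survival design reproduces: 4 × (1.2816 + 0.8416)² / (ln 0.517)² = 41.5, so 42 deaths. Power at 42 deaths is 80.4%, and the critical hazard ratio is exp(−2 × 1.2816/√42) = 0.673. Nothing below changes these.

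**Inputs.** No treatment duration is stated, so these are proxies from the background sections.
- Regorafenib, escalating dose (Section 1.4): the "proportion of patients who initiated the third cycle in the weekly dose escalation arm" was 43%. I take this as 43% still on drug at 8 weeks.
- Anti-EGFR, median progression-free survival: 4.1 months for cetuximab plus irinotecan and 1.5 months for cetuximab alone in irinotecan-unresponsive patients (Section 1.1); 3.7 months for cetuximab and 12.3 weeks for panitumumab in KRAS wild type (Section 1.2).

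**Assumptions.** Time on drug is exponential with stopping rate μ. Progression-free survival stands in for time on anti-EGFR therapy. One month is 4.348 weeks. The event hazard λ is the same in both arms, and 3% per week is illustrative.

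**Formulas.**
- Regorafenib: μ = −ln(0.43)/8 = 0.1055 per week.
- Anti-EGFR: μ = ln 2/median.
- Mean exposure = 1/μ.
- Crude incidence = λ/(λ+μ).
- Incidence by week T, with stopping as a competing event = [λ/(λ+μ)] × [1 − exp(−(λ+μ)T)].

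**Results at λ = 3% per week.** The last column lets the hazard act only in weeks 1 to 4.

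| Drug and proxy | μ per week | Mean weeks | Ratio to regorafenib | Crude incidence | By week 8 | Hazard in weeks 1–4 only |
|---|---|---|---|---|---|---|
| Regorafenib, 43% at week 8 | 0.1055 | 9.5 | 1.0 | 22% | 14.7% | 9.3% |
| Anti-EGFR, 1.5 months | 0.1063 | 9.4 | 1.0 | 22% | 14.6% | 9.3% |
| Anti-EGFR, 12.3 weeks | 0.0564 | 17.7 | 1.9 | 35% | 17.3% | 10.1% |
| Anti-EGFR, 3.7 months | 0.0431 | 23.2 | 2.4 | 41% | 18.2% | 10.4% |
| Anti-EGFR, 4.1 months | 0.0389 | 25.7 | 2.7 | 44% | 18.4% | 10.5% |

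Example for the 12.3-week row: 0.03/(0.03 + 0.0564) = 35%, against 0.03/(0.03 + 0.1055) = 22% on regorafenib.

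At constant hazard the crude gap is 13 to 21 percentage points for ratios of 1.9 to 2.7, and nil at 1.0. An 8-week window cuts it to about 3 to 4 points. For events confined to the first 4 weeks the crude gap is already only about 1 point.

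**Would a rate be safer?** At constant hazard, events per unit of time at risk are equal in both arms. With risk confined to weeks 1 to 4 this fails. First events per patient-month on drug are 0.0926/(9.48/4.348) = 0.042 on regorafenib and 0.018 to 0.025 on anti-EGFR for ratios of 2.7 down to 1.9. Regorafenib would then look about 1.7 to 2.4 times as toxic at identical weekly risk.

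**The case against.** The case for leaving the plan alone has real weight.

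- **The main toxicities are early.** Section 1.4 puts the regorafenib hand-foot reaction in the first 1 to 2 weeks, and Section 1.5 says regorafenib events were most frequent in the first course. Section 1.3 puts acneiform rash at 1 to 3 weeks. This stands, and for such events the distortion is trivial.
- **Unequal durations are inferred.** A reader might conclude that anti-EGFR treatment will last well over twice as long and that arm B will look more toxic throughout. The documents do not support that. The 12.3-week figure gives a ratio of 1.9 and the 1.5-month figure gives 1.0. Section 1.71 reports that about 40% of cetuximab-treated patients in one study progressed within 2 months, which implies a mean of 8.7/−ln(0.6) = 17 weeks and a ratio of 1.8. The proxies are not specific to right-sided tumours, where Sections 1.9 and 16.1 report no first-line survival benefit from anti-EGFR therapy, so they may overstate exposure.
- **The drugs differ in kind.** More paronychia on an anti-EGFR antibody would not be merely an exposure artefact. This stands; the equal-hazard calculation isolates the exposure component and predicts nothing about observed differences.
- **Crude incidence is a legitimate description.** It shows what patients experience on a drug as given. No adverse-event test is named, the decision rule uses overall survival only, and a whole-period summary is planned. All true, but Section 16.12 still promises a comparison by phase. PFS1 and PFS2 give only partial context, because patients also stop for intolerance.

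A reader might also infer that events per patient-month should replace the crude frequency. The last calculation shows why not: that measure can mislead in the opposite direction when risk is front-loaded.

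**Conclusion.** The concern holds in a limited form. The plan compares phase-specific incidence between arms using only a crude count over an open-ended window. If time on drug differs, the longer-treated arm will show more patients with time-accruing events at the same risk.

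The cited figures suggest a difference but do not establish one. The mean exposure ratio of anti-EGFR to regorafenib runs from about 1.0 to 2.7, and the crude gap at 3% per week runs from none to 22% against 44%. This rests on exponential time on drug, progression-free survival as a proxy for treatment time, and a constant, equal hazard. Early events such as hand-foot reaction and acneiform rash are barely affected. In the sequential phase the drugs are swapped, so any effect would run the other way between arms.

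This is a gap in how harm would be interpreted. It does not touch the primary analysis, the 42-death target or the power. It is worth closing because the remedy is cheap and the size of the problem cannot be judged unless exposure is reported.

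**What to change.** In Section 16.326, for each phase and arm:

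1. Report time on treatment (median, range, and proportion still on drug at 8 weeks).
2. Add the cumulative incidence of grade 3 or higher events, and of each solicited event in Section 10.52, over a common window: the first two cycles, 8 weeks from the start of that drug. Treat stopping the drug or death as a competing event.
3. Keep the crude table, and base statements about between-arm toxicity on the two together.
4. If wanted, show events per patient-month as a supplement for late or time-accruing events, but not as the basis of the comparison.

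**Cost.** SAP wording, some programming and a few extra tables. Section 18.1 already has treatment and adverse-event forms submitted at each evaluation. If onset dates are not on those forms, which the documents do not show, the window can be defined by cycle.

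**Downsides.** Events after week 8, including late paronychia, appear only in the crude and rate tables. The 8-week figure reduces the dependence on stopping but does not remove it: about 15% against 17% to 18% at 3% per week.

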16.4 Data & Safety Monitoring

16.41 Review

The study chair(s) and the study statistician will review the study at least twice a year to identify accrual, adverse event, and any endpoint problems that might be developing. The Mayo Clinic Cancer Center (MCCC) Data Safety Monitoring Board (DSMB) is responsible for reviewing accrual and safety data for this trial at least twice a year, based on reports provided by the MCCC Statistical Office.

16.42 Adverse Event Stopping Rules

The stopping rules specified below are based on the knowledge available at study development. We note that the Adverse Event Stopping Rule may be adjusted in the event of either (1) the study re-opening to accrual or (2) at any time during the conduct of the trial and in consideration of newly acquired information regarding the adverse event profile of the treatment(s) under investigation. The study team may choose to suspend accrual because of unexpected adverse event profiles that have not crossed the specified rule below.

Accrual will be temporarily suspended to this study if at any time, in either arm, we observe events considered to be at least possibly related to study treatment (i.e., an adverse event with attribute specified as “possible”, “probable”, or “definite”) that satisfy the following:

If at any time, 3 of the initial 15 treated patients or 20% or more of all patients (i.e. when accrual is greater than 30 patients) have experienced a grade 4+ adverse event.

We note that we will review Grade 4 and 5 adverse events deemed “unrelated” or “unlikely to be related”, to monitor the emergence of a previously unrecognized treatment-related adverse event.

17.0 Pathology Considerations/Tissue Biospecimens

17.1 Tissue Biospecimen Submission

17.11 Summary Table of Tissue Biospecimens for This Protocol

Type of tissue biospecimen to submit	Mandatory or optional	When to submit	Reason for submission (background/methodology section)	Where to find specific details for biospecimen submission
FFPE tissue block with corresponding H&E slide or up to twenty-five (25) 4-micron, unstained slides and up to three (3) corresponding H&E slides from primary tumors present prior to study entry (if available)	Mandatory	Baseline	Correlative studies (Section 17.3)	Section 17.2

17.2 Paraffin Embedded Tissue Blocks/Slides

17.21 Submit one formalin fixed paraffin-embedded (FFPE) tumor tissue block with largest amount of invasive tumor (at least 1 cm of tumor for cases of surgical resection) from original surgery at the time of diagnosis. Biopsy material obtained at the time of metastatic diagnosis may be submitted, if blocks from the surgical resection are inadequate or unavailable. **A corresponding H&E slide for each submitted block must be provided.** The H&E slide for each block should be reviewed by the institution's pathologist to assess tissue quality prior to submission.

17.22 The FFPE tissue block is preferred; however, **if an institution is unable to provide a tissue block**, cut up to 25 (twenty-five) 4-micron sections and mount on charged glass slides. **Label the slides with ACCRU patient ID number, accession number, and order of sections, and thickness of sections.** **NOTE:** do NOT place "sticky" labels directly on slides, **the institution label needs to be visible.** H&E stain every tenth slide (i.e., slides labeled 1, 11, 21, etc.). The H&E slides should be reviewed by the institution's pathologist to assess tissue quality prior to submission. For samples containing less than 7 square millimeters of tumor tissue, multiple sections should be mounted onto each slide to ensure that the appropriate amount of tumor tissue is available. Ideally, each slide should have a minimum of 75% tumor tissue on the slide to be deemed adequate for study. **Do not bake or place covers slips on the slides.**

[figure not shown]
17.23 The following materials below are mandatory (unless indicated otherwise) and required for shipment:

- Paraffin embedded tissue blocks with corresponding H&E slide(s) (OR up to 25 (twenty-five) unstained slides with corresponding H&E slide(s)).
- Specimen Submission: Tissue form

- Surgical Pathology Report
- Operative Report (*optional*)

NOTE: Please include the ACCRU patient ID number on all materials listed above.

- 17.24 The block/slides must be appropriately packed to prevent damage (e.g., slides should be placed in appropriate slide container) and placed in an individual plastic bag. Label the bag with the protocol number, ACCRU patient ID number, and patient initials.
- 17.25 Tissue specimens must be shipped \leq 90 days from date of randomization.
- 17.26 Verify that the appropriate sections of the Specimen Submission: Tissue form are completed and filled in correctly. Enter information from the Specimen Submission: Tissue form into the remote data entry system on the same day the specimen is submitted (see Forms Packet).
- 17.27 Ship all block/slide tissue specimens and accompanying materials to the ACCRU Research Base:

- 17.28 When an appropriate request is submitted, the ACCRU Operations Office will forward the block(s) to the Duke Phase I Biomarker Laboratory located at Duke University for processing as outlined in Section 17.3.
- 17.3 Study Methodology and Storage Information
Submitted tissue samples will be analyzed as follows:
 - 17.31 At the completion of the study, any unused/remaining material will be stored in the Duke Phase I Biomarker Laboratory located at Duke University for future research according to the patient consent permission. Potential future research may include immunohistochemistry (IHC) analyses to analyze predictive biomarkers, changes in expression pattern with therapy, and correlation with response and/or adverse events. When a protocol is developed, it will be presented for IRB review and approval.
 - 17.32 Banking of tumor tissue, according to the patient consent permission, is for future research. As protocols are developed, they will be presented for ACCRU and IRB review and approval. (This collection is part of a general strategy of investigation for ACCRU studies).
 - 17.33 The institutional pathologist will be notified by the Pathology Coordinator if the block may be depleted.

- 17.34 Blocks requested to accommodate individual patient management will be returned promptly upon request.
- 17.35 Return of Genetic Testing Research Results: No genetic specimens will be collected from tissue biospecimens for this study. If future genetic testing is being requested for stored tissue, patient reconsent is required.

